6.4. Visit Windows

For efficacy analysis, the time windows specified in

Table 4 describe how efficacy data will be assigned to protocol-specified time points, as displayed in the Schedule of Assessments in SAP [Section 3.5.1](#). All time points and corresponding time windows are defined based on Dosing Date.

If more than one efficacy observation for a specific assessment is included in a time window, the assessment closer to the nominal time will be used. If there are two efficacy observations equally distant to the nominal time, the latest one will be used in analyses. Any efficacy assessments occurring outside the analysis windows will be considered an assessment of an unscheduled visit.

Table 4: Analysis Time Windows of Bayley Scales, CHOP-INTEND, Development Milestones and Pulmonary Exam*

Scheduled Visit	Nominal Days (Study Day)	Acceptable Analysis Window in Study Days (Min Day – Max Day)
Baseline	-	<1
Month 1	30	1 to 44
Month 2	60	45 to 74
Month 3	90	75 to 104
Month 4	120	105 to 134
Month 5	150	135 to 164
Month 6	180	165 to 194
Month 7	210	195 to 224
Month 8	240	225 to 254
Month 9	270	255 to 284
Month 10	300	285 to 314
Month 11	330	315 to 344
Month 12	360	345 to 374
Month 13	390	376 to 404

Scheduled Visit	Nominal Days (Study Day)	Acceptable Analysis Window in Study Days (Min Day – Max Day)
Month 14	420	405 to 434
Month 15	450	435 to 464
Month 16	480	465 to 494
Month 17	510	495 to 539
Month 18	540	540 to 570
Final Treatment Visit and 14 Months of Age Analysis Window		0 to ≤14 days after patient reaches 14 months of age (420-434 days of age) visit window; 0 to ≤14 days after patient reaches 18 months of age (540 days of age) visit window

*Depending on age at time of dosing, patients will complete varying number of visits. The patient must complete a visit within 2 weeks after reaching 14 months of age; subsequent visits will be scheduled from that visit date. The patient must also complete the final study visit within 2 weeks after reaching 18 months of age.

Due to the difficulty in clinical operation, some landmark visits criteria, like 14 or 18 months of age visits, may not be attained in the protocol defined visit windows. As long as a formal landmark visit cannot be scheduled and the next planned visit is made, for example age of 15 months visit, or survival status is confirmed, for example still survived after age of 18 months, data collected at the unscheduled visit may still be able to map to the landmark visit and included in the corresponding landmark analysis. And protocol deviation will be filed accordingly.

Safety data, such as laboratory results, vital signs, ECGs, and physical exams will be assessed by date and study day. For change from baseline analyses the value associated with the scheduled visit will be used. For summaries of shifts from baseline and potentially significant values all values will be considered for these analyses. Baseline for safety measures will be defined as the latest value before Day 1.

The efficacy data of this study will be compared to the data from the PNCR network. The analysis visit of PNCR will be based on the Visit Month defined in the PNCR dataset.

Table 5: Analysis Time Windows for Dataset from PNCR Network

Scheduled Visit	PNCR
Baseline	≤ Enrollment Date
Month 2	Visit Month 2
Month 4	Visit Month 4
Month 6	Visit Month 6
Month 9	Visit Month 9
Month 12	Visit Month 12
Month 18	Visit Month 18

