1.2. Glossary of Definitions

Abbreviations list pertains to the SAP only.

Abbreviation	Description
AE	Adverse Event: Any untoward medical occurrence in a clinical investigation subject which does not necessarily have a causal relationship with the drug or device under study.
Age	For a given event, age will be expressed in days or months and rounded to one decimal place for months. A month is standardized to a period of 30 days.

Abbreviation	Description
	Age at Event = (Date of Event – Date of Birth + 1)/ 30 (displayed as months). Age at Baseline = (Date of Gene Therapy Infusion – Date of Birth + 1)/ 30 (displayed as months).
Baseline	Baseline, e.g., in terms of baseline laboratory values, vital signs, or physical exam results, refers to a measurement or evaluation made prior to initiation of gene therapy infusion. If there are multiple measurements prior to the initiation of gene therapy infusion, only the latest measurement in most cases will be considered as baseline for analysis purposes or defined specifically.
BiPAP	Bilevel Positive Airway Pressure, a form of non-invasive mechanical pressure support ventilation.
CHOP-INTEND	Children's Hospital of Philadelphia Infant Test of Neuromuscular Disorders, a 16-item motor function assessment validated for use in infants with spinal muscular atrophy.
CMAP	Compound Muscle Action Potential, the total electrophysiological output in a muscle or muscle group recorded by surface electrodes following supramaximal stimulation of the innervating nerve.
Day 1	The day of the gene therapy treatment
Dose	Total vector genome delivered (in vg /patient weight on Day – 1(kg)).
MedDRA	Medical Dictionary for Regulatory Activities is a medical terminology used to classify adverse event information associated with the use of biopharmaceuticals and other medical products.
CTCAE	Common Terminology Criteria for Adverse Events version 4.03. The CTCAE is descriptive terminology, involving a severity scale, which is used for AE reporting in particular for unique patient populations. It is a subset of MedDRA terminology.
Permanent Ventilation	Requirement of \geq 16-hour respiratory assistance per day (includes BiPAP) continuously for \geq 14 days in the absence of an acute reversible illness, excluding perioperative ventilation.
PNCR	Pediatric Neuromuscular Clinical Research Network

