Study Day	For any event of interest, Study Day = calendar date of event – calendar date of gene transfer +1. Day 1 is the Study Day of the gene transfer and any events occurring on the same calendar day as the gene transfer.
TEAE	Treatment-emergent Adverse Event = any adverse event whose onset (or worsening of an existing AE) occurred on or post day of gene therapy infusion.

Abbreviation	Description
Vector genome	The human SMN cDNA sequence, corresponding to the mature mRNA, cloned into the self-complementary AAV vector plasmid.

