6.2.3. Definition of Final Treatment Value

For the purposes of the co-primary endpoint of survival (see [Section 8.1.2](#)), the first non-missing value after the participant reaches 14 months of age. There is no upper bound for the “14 months” age visit; that is, no visit is too late to represent the “14 months of age” analysis. The earliest visit on or after 420 days of age will be used in the “14 months of age” analysis.

For all other endpoints, including the co-primary endpoint of functional independent sitting (see [Section 8.1.1](#)), the co-secondary endpoints of “maintain ability to thrive” (see [Section 8.2.1](#)), “independence of ventilatory support” (see [Section 8.2.2](#)), and [REDACTED]

[REDACTED] the final treatment value for each patient is the first non-missing value on or after the participant reaches 18 months of age (540 days) with an upper limit of 570 days. Thus, the earliest visit between 540 and 570 days of age, inclusive, will be used in the “18 months of age” analysis.

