6.7. Subgroups

Two subgroups based on age at dosing (study day 1) will be assessed in the selected analysis (developmental milestones and statistical modeling parts):

- Patients with age at dosing (study day 1) \leq 4 months (120 days)
- Patients with age at dosing (study day 1) $>$ 4 months (120 days).

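### SAP Table 4 puts the 18-months-of-age limits on the dosing clock, so its Month 18 row is all but empty and its late monthly rows are selected on age at dosing

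*SAP*

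**What the plan says.** Table 4 in SAP 6.4 assigns Bayley, CHOP-INTEND, developmental milestone and pulmonary data to rows for Months 1 to 18. The text above it says: "All time points and corresponding time windows are defined based on Dosing Date". The glossary (1.2) fixes that clock: "Study Day = calendar date of event – calendar date of gene transfer +1". The Month 18 row has nominal Study Day 540 and window 540 to 570.

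Other parts of the SAP run on age:

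- The last row of Table 4 gives windows for the 14- and 18-months-of-age visits in days of age, starting at 420 and 540 and lasting up to 14 days.
- Section 6.2.3 says that for the 18-month analysis "the earliest visit between 540 and 570 days of age, inclusive, will be used".
- Section 3.5 and Table 1 make the 18-months-of-age visit the End of Study visit, due no more than 14 days after that age is reached.
- Sections 3.5 and 5.2 require dosing before 180 days of age.

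The Table 4 footnote concedes: "Depending on age at time of dosing, patients will complete varying number of visits". Section 6.7 states: "Two subgroups based on age at dosing (study day 1) will be assessed in the selected analysis". It cuts at 120 days and names milestones and modeling as the analyses concerned. For the natural history data, 6.4 says: "The analysis visit of PNCR will be based on the Visit Month defined in the PNCR dataset". Table 5 lists a Visit Month 18.

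**The concern.** Monthly rows count from infusion, while follow-up stops at a fixed age. The last Study Day an infant can reach therefore depends on how old that infant was at dosing. A Month 18 row on the dosing clock asks for 18 months of follow-up after treatment, which the design gives to almost nobody.

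The rows before it lose infants from the older end of the dosing-age range by design, not at random. Age at dosing is the factor the plan itself uses to form subgroups. A rise across late rows could thus reflect a change in who is still present rather than further improvement.

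Two values would also carry nearly the same name, Month 18 and 18 months of age, yet describe different infants and visits. Section 6.2.4.1 refers to Tables 4 and 5 for the sitting videos, so a programmer could pick up the wrong row.

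**Working it through.** **Inputs**

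- Month length: "A month is standardized to a period of 30 days" (1.2).
- Age at dosing, A: "Age at Baseline = (Date of Gene Therapy Infusion – Date of Birth + 1)/ 30", taken here in days before division by 30.
- Largest A: 179 days (3.5, 5.2).
- Last age at follow-up, E: 540 to 554 days (3.5, Table 1, last row of Table 4); 570 as the upper limit in 6.2.3.
- First Study Day of each row, S: Table 4.

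**The plan's own figures.** 18 × 30 = 540 and 14 × 30 = 420, as stated. From Month 2 to Month 16 each window runs from nominal day − 15 to nominal day + 14 (Month 16: 480 − 15 = 465, 480 + 14 = 494), except the start of Month 13. That rule would give Month 17 as 495 to 524 and Month 18 as 525 to 554. Table 4 prints 495 to 539 and 540 to 570. The latter pair equals the age limits of 6.2.3, which suggests that age limits were entered in a Study Day column.

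**Reach of each row.** Ages and Study Days both count the first day as 1, so Study Day = age at visit − A + 1. The last possible Study Day is E − A + 1, and a row starting at S can be reached only if A ≤ E + 1 − S. Largest dosing age, in days:

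| Row | S | E = 540 | E = 554 | E = 570 |
|---|---|---|---|---|
| Month 12 | 345 | 196 | 210 | 226 |
| Month 13 | 376 | 165 | 179 | 195 |
| Month 14 | 405 | 136 | 150 | 166 |
| Month 15 | 435 | 106 | 120 | 136 |
| Month 16 | 465 | 76 | 90 | 106 |
| Month 17 | 495 | 46 | 60 | 76 |
| Month 18 | 540 | 1 | 15 | 31 |

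A value of 179 or more means that every eligible infant can reach the row. Month 12 is the last row for which this holds under all three values of E.

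**At the subgroup cut, E = 554.** An infant dosed at 120 days can reach Study Day 554 − 120 + 1 = 435, the first day of Month 15. One dosed at 121 days stops at 434.

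**The gap.** Month 12 ends at 374 and Month 13 starts at 376. The End of Study visit falls on Study Days 541 − A to 555 − A. This range includes 375 for A from 541 − 375 = 166 up to 179, the oldest dosing age allowed.

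**Share of infants, illustration only.** The document gives no distribution of dosing age. I assume it uniform from 1, 15 or 30 days up to 179, with E = 554. The share able to reach Month 15 is then 67%, 64% or 61% (120/179, 106/165, 91/150). For Month 18 it is 8.4%, 0.6% or 0% (15/179, 1/165, 0/150). With E = 570 the Month 18 shares are 17.3%, 10.3% or 1.3%.

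**The case against.** Several points on the other side are sound.

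- **No confirmatory analysis is touched.** A reader might infer from an unreachable Month 18 that the sitting endpoint cannot be measured. It can. Section 6.2.3 windows sitting, ability to thrive and ventilatory independence at 540 to 570 days of age, and takes survival at the first visit from 420 days of age.
- **A visit on Study Day 375 is not lost.** If it is the End of Study visit, the age-based last row of Table 4 captures it, and 6.4 also lets unscheduled visits be mapped to a landmark. It drops out only of the monthly rows, and only on that one day.
- **The 120-day limit is not absolute.** A reader might infer that Months 15 to 18 can never hold an infant dosed after 4 months. That is true for visits by day 554. With the 570-day cap, Month 15 admits infants dosed up to day 136.
- **The affected displays are largely out of sight.** Section 8.3 is redacted. No visible text sets out by-visit curves, a subgroup comparison at Month 15 or later, or a pairing of Month 18 with the natural history Visit Month 18. The summary of changes (21.5) mentions models with age subgroup as covariate. A claim that such results will be biased goes beyond the document.
- **Time since dosing is a natural axis** for response to a single infusion, and the footnote discloses that visit numbers vary.

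These points narrow the harm but do not correct the table. The footnote neither makes the Month 18 row usable nor says how the selected late rows should be read. The dosing-date sentence still contradicts the last row of its own table.

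**Conclusion.** Table 4 is wrong as written in three respects: the Month 18 row carries age limits on the dosing clock, the sentence putting every window on the dosing date conflicts with the age-based last row, and Study Day 375 has no monthly row. Followed literally, it gives a Month 18 row open only to infants dosed by day 15 of life (day 31 at the 570-day cap) and rows from Month 14 onward selected on age at dosing.

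The limits rest on the SAP's 30-day month and on End of Study by 554 days of age; the 570-day cap raises each by 16 days. The damage is confined to by-visit summaries of Bayley, CHOP-INTEND, milestones and pulmonary exam, and to any by-visit comparison that uses Month 18. The arithmetic is certain. How much any reported result would move cannot be judged from the visible text.

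**What to change.** In SAP 6.4 and Table 4:

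1. Start Month 13 at Study Day 375.
2. Replace the Study Day row for Month 18 by the 18-months-of-age window of 6.2.3, labelled as days of age.
3. Restrict the dosing-date sentence to the monthly rows, so that it agrees with the age-based last row.
4. Show the late dosing-anchored rows (Month 13 or 14 onward) with their n and the range of dosing ages they can contain, or present those data by age.

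The cost is a wording change and minor reprogramming of the visit derivation. Age is already derived from the date of birth, so no new data are needed, and no endpoint, test or sample size changes. If the late data are shown by age, the displays carry a second time axis, and each age point mixes different times since treatment.

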- s If a Day -1 CHOP-INTEND assessment is not completed, a CHOP-INTEND assessment should be completed on Day 1 prior to dose administration.
- t for patients enrolled in the study prior to amendment 3 and irrespective of study schedule, after signing an updated informed consent form, an echocardiogram, 24-hour Holter monitoring, and 12-lead ECG will be performed at the next scheduled visit and then in accordance with the Schedule of assessments Compound Motor Action Potential Manual

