6.2. Key Definitions

6.2.1. Definition of Baseline

The baseline value refers to the last non-missing measurement collected before gene therapy infusion of study drug. On Study Day 1, all assessments should be performed prior to administering the gene therapy infusion of study drug per protocol. The baseline value is therefore determined by the last non-missing measurement collected on or before the first day of study drug administration. If multiple measurements are recorded on the same day, the last measurement recorded prior to the gene therapy infusion will be used as the baseline value. If these multiple measurements occur at the same time or time is not available, then the average of these measurements (for continuous data) or the worst among these measurements (for categorical data) will be considered as the baseline value. This same baseline value will be used for the treatment and post-treatment periods. For some special measures, the baseline value will be defined explicitly in the corresponding section.

The baseline values will be the first non-missing values collected for the control patients from the PNCR dataset.

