10.4.3. Statistical Methods

Clinical laboratory test will be summarized at each visit during the treatment period. The baseline value will be the last measurement on or before the day of the infusion of study drug. This same baseline value will be used for all changes from baseline tables in the treatment period and post-treatment period. Natural history control data is not available for this evaluation.

Mean changes from baseline to End of Study/Early Termination will be summarized for each protocol-specified laboratory parameter with the baseline mean, visit mean, change from baseline mean, standard deviation, minimum, maximum, and median.

During the treatment period, laboratory data values will be categorized as low, normal, or high based on normal ranges of the laboratory used in this study. Shift tables from baseline to minimum value, maximum value, and final values during the treatment period will be created. The shift tables will cross tabulate the frequency of patients with baseline values below/within/above the normal range versus minimum/maximum/final values below/within/above the normal range.

The number and percentage of patients with post-baseline values during the treatment period meeting the specified criteria for Potentially Clinically Significant (PCS) laboratory values will be summarized. A post-baseline value must be more extreme than the baseline value to be considered a PCS finding. A listing will be provided that presents all of the lab values for the patients meeting PCS criteria during treatment Period.

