10.5. Vital Signs

Vital signs (pulse, respiration, temperature, diastolic blood pressure, body weight, systolic blood pressure, pulse oximetry) will be examined at each visit. Clinically-significant, treatment-emergent findings will be reported as adverse events.

A summary of changes from first recorded value in vital signs will be described at each visit on the safety set. In addition, vital signs results will be flagged as Potentially Clinically Significant (PCS) if they meet the pre-specified criteria. The number and percent of patients meeting each PCS criterion will be summarized starting at Day 1 and continuing through the end of study.

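### The safety baseline in Section 6.4 (latest value before Day 1) contradicts the general rule in Section 6.2.1, and the two rules, with Section 10.5 and Table 4, pick different reference records

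*SAP*

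**What the plan says.** The general rule is in SAP Section 6.2.1: "The baseline value refers to the last non-missing measurement collected before gene therapy infusion of study drug". The section goes on: "The baseline value is therefore determined by the last non-missing measurement collected on or before the first day of study drug administration". When several values fall on one day, "the last measurement recorded prior to the gene therapy infusion will be used as the baseline value". The glossary (Section 1.2) also ties baseline to the start of the infusion. A Day 1 pre-dose value is therefore eligible. Section 6.2.1 has an exception clause: "For some special measures, the baseline value will be defined explicitly in the corresponding section".

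Section 6.4 introduces safety data, naming laboratory results, vital signs, ECGs and physical exams, and then states: "Baseline for safety measures will be defined as the latest value before Day 1". Day 1 is the day of infusion (Sections 1.2 and 6.2.2).

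Other sections give their own reference:
- Section 10.4.3, labs: "The baseline value will be the last measurement on or before the day of the infusion of study drug".
- Section 10.5, vital signs including body weight: "A summary of changes from first recorded value in vital signs will be described at each visit on the safety set".
- Section 10.6, ECG: the mean of all measures in the 6 hours before dosing.
- Table 4 (Section 6.4), efficacy windows: Baseline is study day <1 and Month 1 is days 1 to 44. Yet footnote s to Table 1 says that, if the Day -1 test is missed, "a CHOP-INTEND assessment should be completed on Day 1 prior to dose administration".

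**The concern.** Sections 6.2.1 and 6.4 cover the same safety data, give different rules and set no order of precedence. Footnote b to Table 1 makes Day 1 assessments pre-dose, so Day 1 records that are valid baselines under Section 6.2.1 will exist and Section 6.4 throws them out. Whoever programs the datasets has to choose, in an open-label study where the data can be seen.

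The choice matters because the patients are infants under 180 days old at dosing. Weight and head circumference are still increasing. A reference taken at Screening counts growth before dosing as change after it. Shift tables for physical exam and change tables for vital signs and ECG also move with the reference. For labs, a post-baseline value counts as potentially clinically significant (PCS) only if it is more extreme than baseline, so a different baseline can change who is counted.

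**Working it through.** The point rests on no sample size, power or alpha figure, so there is none to reproduce. The check applies each rule to the Table 1 schedule.

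**Inputs.** Screening runs from Day -30 to Day -2. Physical exam is scheduled at Screening and Day 1, not Day -1. Vital signs and ECG are scheduled at Screening, Day -1 and Day 1. CHOP-INTEND is scheduled at Screening and Day -1, with Day 1 pre-dose as fallback. Labs are marked at Screening and Day -1, but footnote o, attached to the Day -1 mark in the table as extracted, speaks of samples on Day 1 before dosing.

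**Record selected as reference**

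| Data | Section 6.2.1 | Section 6.4 | Own section |
|---|---|---|---|
| Physical exam, head circumference | Day 1 pre-dose | Screening | none |
| Vital signs, weight | Day 1 pre-dose | Day -1 | 10.5: first recorded (Screening) |
| ECG | defers to 10.6 by the exception clause | Day -1 | 10.6: mean over 6 hours pre-dose |
| Labs, if a Day 1 pre-dose sample exists | Day 1 | Day -1 | 10.4.3: Day 1 |
| Labs, if drawn only on Day -1 | Day -1 | Day -1 | 10.4.3: Day -1 |
| CHOP-INTEND, Day -1 missed | Day 1 pre-dose | Table 4 (<1): Screening | none |

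**ECG window.** The window opens at infusion time minus 6 hours. For an infusion at or after 06:00 that is 00:00 or later on Day 1, so the whole window lies on a day that Section 6.4 excludes. The two rules then share no record.

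**CHOP-INTEND window.** A Day 1 score falls in the Month 1 window (1 to 44). Section 6.4 reports the value nearest the nominal day, 30. Distances are 30 - 1 = 29 for Day 1, against 23, 16, 9 and 0 for the scheduled Days 7, 14, 21 and 30. Day 1 would be reported as Month 1 only if all the later scores in the window were missing. The practical loss is the baseline, which falls back to Screening.

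**Illustration with assumed values** (not trial data). Screening 100; Day -1 110; Day 1 at 4 hours pre-dose 124; Day 1 at 1 hour pre-dose 130; post-dose 120. Change = post-dose value minus baseline.
- Section 6.2.1: 120 - 130 = -10.
- Section 6.4: 120 - 110 = +10.
- Section 10.5: 120 - 100 = +20.
- Section 10.6: baseline (124 + 130)/2 = 127, and 120 - 127 = -7.

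Read by data type, a vital sign changes by -10, +10 or +20 and an ECG measure by +10 or -7. A lab with a Day 1 sample is not more extreme than baseline in the high direction under Section 10.4.3 (120 < 130) but is under Section 6.4 (120 > 110). The sign of change and the PCS precondition can both flip.

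**Size of one PCS reclassification.** With at most 20 patients, one patient is at least 1/20 = 5 percentage points.

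**The case against.** The best defence is that the SAP expects measure-specific baselines. The exception clause in Section 6.2.1 covers the ECG average in Section 10.6, and Section 10.5 can be read as a choice of reference for vital signs that does not redefine baseline. That stands for Section 10.6. It does not rescue Section 6.4, which is a blanket rule for the same safety data, carries no exception, and conflicts with Sections 10.5 and 10.6 as well as with 6.2.1.

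Several stronger readings are tempting and are not supported:
- **Four incompatible definitions.** Sections 6.2.1 and 10.4.3 agree in practice, and no data type is subject to four rules.
- **A post-infusion lab could become baseline under Section 10.4.3.** The wording is loose, but footnotes b and o place Day 1 samples before dosing, and the next scheduled lab is Day 2.
- **A Day 1 CHOP-INTEND would become the Month 1 result.** The nearest-to-nominal rule makes this rare.
- **PCS results in general depend on the baseline rule.** Only laboratory PCS does. Vital-sign PCS uses pre-specified criteria, ECG PCS is identified by the central reviewer, and the combined liver criteria apply whatever the baseline.

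It is also fair to say that 30 days is the longest screening interval, not a typical one, and that the affected safety tables are descriptive.

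**Conclusion.** The contradiction is real and should be corrected. Sections 6.2.1 and 6.4 select different baselines for physical exam and vital signs. Section 6.4 also conflicts with the ECG rule in Section 10.6. Section 10.5 adds a third and older reference for vital signs and weight, and Table 4 excludes a CHOP-INTEND score that footnote s permits.

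The reach is limited to safety change and shift tables, head-circumference and weight change, and the CHOP-INTEND baseline wherever it is used. Laboratory PCS counts are touched only if a Day 1 pre-dose sample is drawn, which the table mark and footnote o leave unclear and which may be an extraction fault.

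A reader might infer that the efficacy conclusions are at risk. They are not. The co-primary and co-secondary endpoints are binary states at 14 or 18 months of age. Section 6.3 does require a non-missing baseline for inclusion, but the milestone, swallowing and pulmonary assessments are scheduled before Day 1, so a patient assessed on schedule meets that requirement under either rule.

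**What to change.** Keep Section 6.2.1 as the single rule: the last non-missing value before the start of infusion, including Day 1 pre-dose. Then:
- delete the baseline sentence in Section 6.4 or replace it with a reference to Section 6.2.1;
- in Section 10.5, report change from baseline;
- in Table 4, let Baseline include Day 1 pre-dose and start Month 1 after the infusion;
- in Section 10.4.3, replace the day-of-infusion wording with before the start of infusion;
- name the 6-hour ECG average in Section 10.6 as the retained exception, so that the single rule does not silently override it.

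The cost is a few sentences in the SAP and one derivation in the analysis datasets. No data collection changes.
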